12.7.1.3 Vital Signs

Vital sign values will be considered potentially clinically significant if they meet either the low or high potentially clinically significant criteria listed in Table 7. The number and percentage of participants with any potentially clinically significant post-baseline value overall and by each criteria will be tabulated.

Table 7 Criteria for Potentially Clinically Significant Vital Signs

Vital Sign Parameter (unit)	Lower Limit	Upper Limit
Pulse rate (beats per minute)	< 45	> 130
Systolic blood pressure (mmHg)	< 80	> 155
Diastolic blood pressure (mmHg)		> 100
Temperature (°C)		≥ 39.0

A graphical display of each parameter by time point will be presented similarly to laboratory data.

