### ***7.4.3 Vital Signs***

Vital signs will be performed at screening, pre-vaccination and post-vaccination (at the end of the observation period) at the vaccination visit, at all visits during the follow-up and the end of study visit. At each timepoint blood pressure, pulse rate and temperature, will be measured after the participant has been in a sitting position for 5 minutes.

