#### 10.2.2.6.3 Vital Signs

Absolute and change from baseline vital sign results, including the worst change for each variable for each participant will be summarised using descriptive statistics. Treatment emergent out of range results with the corresponding normal ranges, baseline results and clinical significance will be separately listed. Shift tables will be used to show changes from baseline at each timepoint and the worst change in each participant and scatterplots of the worst change will be produced. The number of participants with treatment emergent clinically significant results will be summarised.

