10.2 Baseline and Change from Baseline

Baseline is defined as the last non-missing assessment taken prior to the first dose of study vaccine.

Change from baseline is defined as:

$$\text{Observed result at nominal time point} - \text{observed result at baseline}$$

Change from baseline on the log scale is defined as $\log_{10} T1 - \log_{10} T0$.

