10.10 Multiple Assessments at a Time Point

If a participant has more than one assessment taken at the same time point (e.g. laboratory results, vital signs), for baseline the latest date and time prior to first study vaccination is used. For post-baseline visits, the worst clinical value in the direction of the toxicity presented will be used in the analysis for that time point. All values will be listed.

In cases where solicited AE or daily temperature records are recorded on both the eDiary and CRF with the same date/time, for the primary analysis we will select the CRF record to use. If the solicited AE or daily temperature record was only collected on either the eDiary or the CRF, then all records will be considered for the primary analysis.

For a sensitivity analysis, all records including records identified as duplicates will be used. All records will be listed.

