12.7.1 Primary Endpoints

The primary endpoints are:

- Safety and reactogenicity of the vaccine(s): incidence of AEs, SAEs, \geq Grade 3 study vaccine-related AEs within 4 weeks of vaccination
- Safety of the vaccines with nivolumab: incidence of AEs, SAEs, \geq Grade 3 AEs within 4 weeks of dosing
- Incidence of AESI
- Number and proportion of participants reporting TEAEs within each treatment group
- Number and proportion of participants within each treatment group with potentially clinically significant laboratory values and vital signs within each treatment group
- Change from baseline in laboratory tests and vital sign measurements to each time point of collection

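### The primary count of potentially clinically significant vital signs ignores baseline, so participants already beyond a limit before dosing are not separated from new cases

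*SAP*

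**What the plan says.** The count is one of the primary endpoints in SAP 12.7.1: "Number and proportion of participants within each treatment group with potentially clinically significant laboratory values and vital signs within each treatment group".

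SAP 12.7.1.3 defines a case by level alone: "Vital sign values will be considered potentially clinically significant if they meet either the low or high potentially clinically significant criteria listed in Table 7". Those limits are pulse below 45 or above 130, systolic pressure below 80 or above 155, diastolic pressure above 100, and temperature of 39.0 °C or more. The tabulation rule follows: "The number and percentage of participants with any potentially clinically significant post-baseline value overall and by each criteria will be tabulated".

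SAP 10.2 defines a baseline ("Baseline is defined as the last non-missing assessment taken prior to the first dose of study vaccine"), but 12.7.1.3 does not use it. Where a post-baseline time point has several readings, SAP 10.10 says that "the worst clinical value in the direction of the toxicity presented will be used in the analysis for that time point", so a normal repeat does not cancel a high first reading.

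Protocol 7.4.3 sets the measurement times: "Vital signs will be performed at screening, pre-vaccination and post-vaccination (at the end of the observation period) at the vaccination visit". Later follow-up visits and the end-of-study visit are added to these. Protocol 10.2.2.6.3 describes the corresponding summary: "The number of participants with treatment emergent clinically significant results will be summarised".

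**The concern.** Protocol 4.2 and 4.3 set no numeric limit on blood pressure or pulse. A participant with a systolic pressure above 155 before the first dose can be enrolled, and becomes a case as soon as any one later reading is above 155. In the table that carries the primary count, that person looks the same as someone whose pressure rose after vaccination or nivolumab.

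Every group receives vaccine, so there is no untreated group to show the background rate. The groups are small. SAP 6.1 also reduces vital signs from descriptive summaries of change to listings, so this count carries more of the vital-sign reporting than the protocol intended. At stake is whether a reader, and in particular the DMC, can tell new abnormalities from old ones in this table.

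**Working it through.** **The plan's own figure.** The documents give no design figure for this endpoint. The only one is in SAP 8.1: an 80% chance of seeing an event of 10% incidence in 16 participants. It reproduces: 1 − 0.9^16 = 81.5%.

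**Weight of one case.** SAP 8.1 gives 10 participants in Group 1 and 9 in Group 4; 16 are planned for Groups 2 and 3. One case is 1/9 = 11.1%, 1/10 = 10.0% or 1/16 = 6.3%.

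**Number of readings.** From Protocol Table 2 and Section 7.4.3: Day 0 post-dose, Day 7, Day 28 pre-dose, Day 28 post-dose, Day 35, and Months 3, 6 and 9. That makes 8 scheduled post-baseline readings, plus any unscheduled ones.

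**One participant with a stable usual systolic pressure u.** With within-person SD s and no treatment effect, the chance of at least one of 8 readings above 155 is 1 − Φ((155.5 − u)/s)^8. For u = 140 and s = 8: (155.5 − 140)/8 = 1.94, Φ = 0.974, and 1 − 0.974^8 ≈ 0.19. The range of s is an assumption.

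| Usual systolic (mmHg) | s = 6 | s = 8 | s = 10 | s = 12 |
|---|---|---|---|---|
| 120 | 0.0% | 0.0% | 0.2% | 1.2% |
| 130 | 0.0% | 0.6% | 4.2% | 12.7% |
| 140 | 3.8% | 19.2% | 39.3% | 56.3% |
| 150 | 79.5% | 89.5% | 93.6% | 95.6% |

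Noise almost never makes a case of someone near 120. Someone with borderline or high usual pressure often becomes one.

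**Whole group, systolic above 155 only, no treatment effect.** This is a simulation of 400,000 participants per scenario (person mean plus visit noise; one baseline and 8 later readings). All means and SDs are assumed.

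| Mean | Between / within SD 12 / 8 | 14 / 9 | 15 / 10 |
|---|---|---|---|
| 122 | 4.8% | 9.0% | 12.4% |
| 128 | 11.4% | 17.2% | 21.4% |

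Counting only participants at or below 155 at baseline lowers the range from 4.8–21.4% to 4.0–15.7%. The share of counted participants already above the limit at baseline is therefore about (4.8 − 4.0)/4.8 = 17% at the low end and (21.4 − 15.7)/21.4 = 27% at the high end. Simulated directly, the low end is 16%.

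**Wider assumptions, systolic above 155 or diastolic above 100.** The share counted is 2.1%, 15.5% and 35.4% under low, middle and high assumptions, or 0.3, 2.5 and 5.7 per 16. Excluding those beyond the limit at baseline gives 0.3, 2.1 and 4.6 per 16.

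**Where the baseline split is shown.** The Table 7 limits equal the Grade 3 entry points in Protocol Appendix 1 for pulse, systolic pressure, diastolic pressure and fever. The SAP 12.7.2.4 shift tables cross-tabulate baseline grade with worst post-baseline grade on that scale, so their Grade 3-or-higher part is essentially this count split by baseline. SAP Section 16.0 marks Table 14.3.4.1 (the count) for the DMC and not for the interim analysis. It lists no vital-sign shift table, plot or listing for either.

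**The case against.** The strongest reply is that the split already exists: the final report will contain shift tables on the same cut-offs, by-participant plots and listings, and with groups of 9 to 16 each case can be inspected. That stands for the final report. It does not stand for Table 14.3.4.1 read alone, or for the DMC outputs as listed.

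Four stronger readings are tempting, and the documents do not support them.

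- **That the SAP dropped a worsening requirement set by the protocol.** Protocol 10.2.2.6.3 does refer to treatment-emergent results, but Protocol 10.2.2.6 and SAP 10.6 define that term by timing only. Post-baseline in SAP 12.7.1.3 covers essentially the same window.
- **That most counted cases are pre-existing hypertension.** Under the assumptions above, roughly 73% to 84% of counted participants were not above 155 at baseline. Anyone above the limit is also not automatically eligible: exclusion criteria 1, 23 and 26 leave room for investigator judgement, and eligibility is re-checked on Day 0.
- **That a minimum rise or a second high reading should be a condition.** A rise of 20/10 mmHg has no source in the documents. After the post-dose reading the next scheduled one is about a week later, so a brief move from 140 to 158 (a rise of 18, unlikely to be repeated) would be lost. If baseline at or below the limit is required, plus either a 20 mmHg systolic rise or a second high reading, the modelled no-effect rate is still 2.4% to 11.7%. A sensitive single-reading screen is a legitimate choice in a first-in-human combination study.
- **That false between-group differences follow.** Safety is summarised descriptively and no test is planned on this count. The harm is a number that is hard to read, not a raised error rate.

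**Conclusion.** The point holds as a small reporting gap. A primary safety count includes participants who were already beyond the limit before dosing, and the table that reports it does not show who they are. In Groups 4 and 1, one such participant is 11% or 10%. On assumed systolic distributions with no treatment effect, 5% to 21% of participants would be counted over 8 readings, and about 16% to 27% of those were above 155 at baseline. With diastolic pressure added and wider assumptions, the counted share runs from 2% to 35%.

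These sizes rest wholly on assumed means and SDs and on no screening out by investigators. The textual finding does not. Showing baseline status removes only a minority of no-effect cases; its value is that old and new values can be told apart where the count is read, above all in the DMC package.

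**What to change.** In SAP 12.7.1.3 and Table 14.3.4.1:

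1. Keep the present count unchanged.
2. Add a column with the number of participants meeting each criterion at baseline.
3. Add a row for participants newly meeting each criterion, with those not meeting it at baseline as the denominator.
4. If wanted, add a minimum-change or repeat-reading row, labelled as supportive. It should not replace the count or act as a condition for it.

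Because Table 14.3.4.1 is already on the DMC list, this also closes the gap there.

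The cost is SAP wording and a little more table programming; no new data are needed. One downside remains: a participant already beyond a limit who worsens further appears in the retained count, the listing and the plots, but not in the new-case row.

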12.7.2 Other Safety Endpoints

12.7.2.1 Other Adverse Events

An overall summary of treatment-emergent adverse events, including the number of events reported, will be provided for:

- Any AEs
- Any AEs within 28 days of first vaccination
- Any AEs within 28 days of second vaccination
- Any grade 3 or greater AEs within 28 days of first vaccination
- Any grade 3 or greater AEs within 28 days of second vaccination
- Any AEs related to study vaccines
- Any AEs related to nivolumab

- Any AEs related to study vaccines or nivolumab
- Any grade 3 or greater AEs related to study vaccines
- Any grade 3 or greater AEs related to nivolumab
- Any grade 3 or greater AEs related to study vaccines or nivolumab
- Any AEs with outcome of death
- Any serious AEs
- Any serious AEs related to study vaccines
- Any serious AEs related to nivolumab
- Any serious AEs related to study vaccines or nivolumab
- Any AEs leading to discontinuation of study vaccines
- Any AEs leading to discontinuation of nivolumab
- Any AEs leading to discontinuation of study vaccines or nivolumab
- Any AEs of special interest

Deaths will be identified using the AE eCRF.

In addition, individual summary tables by SOC and PT will be provided for each category (with the exception of any AEs with outcome of death) in the overall TEAE table and presented similarly to the primary endpoint in Section 12.7.1.1. A by-participant summary of all TEAEs leading to death, serious TEAEs, and TEAEs leading to discontinuation of study vaccines or nivolumab will be produced.

AEs leading to discontinuation of study vaccines or nivolumab are defined as any AE with Action Taken with Study Vaccines = 'Drug Withdrawn' or Action Taken with Nivolumab = 'Permanently Discontinue' recorded on the Unsolicited AEs eCRF.

TEAEs will be further summarised by maximum severity (grade 1, grade 2, grade 3, grade 4, grade 5) within each SOC and PT. Participants with multiple events within a particular SOC or PT will be counted under the category of their most severe event within that SOC or PT.

Non-treatment-emergent AEs will be presented by SOC and PT.

All adverse events (including non-treatment-emergent events) recorded on the eCRF will be listed separately.

12.7.2.2 Solicited Adverse Events

For each solicited symptom (grouped by local symptoms and systemic symptoms), the number and percentage of participants reporting an event will be summarised by vaccination (first vaccination, second vaccination) and overall.

For participants experiencing a solicited symptom (i.e. reporting a severity Grade 1 or higher), an additional summary of solicited symptoms by maximum severity after each vaccination (first vaccination, second vaccination) and overall will be presented.

Percentages for both analyses are based on the number of participants reporting the severity of any solicited symptom on any day within the 7-day reactogenicity period following each vaccination (as defined in Section 10.5.5).

Both analyses will be presented for the primary analysis and repeated for the sensitivity analysis (as defined in Section 10.10).

Solicited AEs, local and system reactogenicity, and diary body temperature will be listed separately. A combined listing including solicited symptoms from both the eDiary and CRF for the 7-day reactogenicity period will also be presented.

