**Table 2 Overall Schedule of Assessments at Each Study Visit**

Visit/Call	Screen	Vaccination Clinic	Telephone Call	Clinic	Vaccination Clinic	Telephone Call	Clinic			End of Study / Early Discontinuation Clinic
Timepoint (window)	Day						Month			
	-42 to -1	0	1 (+1d)	7 (±1d)	28 (+2d)	29 (+1d)	35 (±1d)	3 (±7d)	6 (±7d)	9 (±7d)
Informed consent	X									
Baseline/eligibility variables										
Demographics	X									
Inclusion and exclusion criteria	X									
Height and weight	X									
Medical and disease history	X									
HIV, HCV, HBV (quantitative HBV DNA and quantitative HBsAg), HDV serology	X									
Urinalysis	X									
Urine drug screen	X									
Urine pregnancy test (β-hCG)	X	X [a]			X [a]			X [f]	X [f]	X
Laboratory eligibility and safety tests										
Haematology	X	X [a]		X	X [a]		X	X	X	X
Biochemistry	X	X [a]		X	X [a]		X	X	X	X
Liver function tests	X	X [a]		X	X [a]		X	X	X	X
Study vaccination										
Vaccination dose		X			X			X [g]		
Post-dose observation		X			X			X [g]		
Nivolumab dose (Group 3 only) [b]					X					
Other safety assessments										
Full physical examination	X	X [a]			X [a]			X [a]		X
Symptom-directed physical examination				X			X	X	X	
Vital signs	X	X		X	X		X	X	X	X
Local/systemic reactogenicity		X [c]	X	X	X [c]	X	X	X [c]		
Unsolicited adverse events [d]	X	X	X	X	X	X	X	X	X	X
Serious adverse events and adverse events of special interest	X	X	X	X	X	X	X	X	X	X
Prior and concomitant medications	X	X	X	X	X	X	X	X	X	X
Blood for HBV disease markers [e]		X [a]		X	X [a]		X	X	X	X
Immunogenicity assessments										
Blood for cellular immunogenicity assessments		X [a]		X	X [a]		X	X [a]	X	X

[a] Pre-vaccination on Day 0, Day 28, and Month 3 (for UK participants having an MVA-HBV boost)

[b] Participants in Group 3 will receive nivolumab on Day 28. Group 4 is now closed. The patients will be observed for 30 minutes after vaccination. If there are no safety concerns (vital signs and reactogenicity), nivolumab will be infused over 30 minutes and the patients will be observed in the study centre for a further 30 minutes post-infusion.

[c] Captured pre-vaccination and post-vaccination on Days 0 and 28, and Month 3 (for UK participants having an MVA-HBV boost), via eDiaries for 7 days post-vaccination and then at the clinic assessment 7 days post-vaccination (Day 7 or 35)

[d] Recorded in the eCRF from the date the informed consent is signed, at all clinic visits to cover the period since the previous visit and during the visit

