## **6.2 Treatment Day Assessments (Day 0, Day 28 and Month 3 [MVA-HBV Boost (UK participants only)])**

The following will be performed pre-vaccination:

- Re-check of eligibility criteria (Day 0 only)
- A urine pregnancy test will be performed
- Blood samples will be taken for haematology, biochemistry and LFTs
- A full physical examination will be performed
- Vital signs (pulse rate, blood pressure and temperature) will be measured
- A baseline assessment of local and systemic reactogenicity will be performed (see [Appendix 1](#))
- Blood samples will be taken for immunogenicity assessments and HBV disease markers

Participants will then receive study vaccine by intramuscular injection in the non-dominant arm, and will be observed for 30 minutes post vaccination for safety concerns. Nivolumab will then be administered via an infusion, if applicable, according to [Table 1](#). All participants will be assessed in the clinic for at least 30 minutes post-vaccination and post-nivolumab infusion in case of immediate adverse events. The first participant in each cohort will be observed for 1 hour. In the first cohort, the second participant will not be dosed until 48 hours after the first sentinel participant.

The following will be performed post-vaccination:

- The vaccination site will be covered with a sterile dressing during the observation period; it will then be removed and disposed of as GMO waste
- Vital signs (pulse rate, blood pressure and temperature) will be measured at the end of the observation period
- Local and systemic reactogenicity will be assessed at the end of the observation period
- On Day 0, an eDiary, tape measure and thermometer will be provided to perform self-assessment of local and systemic reactogenicity for 7 days after the vaccinations. Participants will be reminded to do the following daily for the 7 days after each vaccination:
  - Take and record their temperature
  - Measure and record the size of vaccination site redness
  - Assess the other solicited adverse events listed in the eDiary

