##### *7.4.1.1 Solicited Adverse Events*

Solicited adverse events are events the participant is specifically asked about. These adverse events are commonly observed soon after receipt of vaccines and relate to local and systemic signs and symptoms. Solicited adverse events will be collected daily in the eDiary for 7 days post-vaccination.

For this study, solicited adverse events to be collected include:

- Vaccination site reactions: pain, induration, warmth, erythema (redness)
- Systemic adverse events: feverishness, chills, myalgia, fatigue, headache, nausea, arthralgia, malaise

Participants will be asked to record the presence of these symptoms and grade the severity as described in [Section 8.2.4.1](#). Oral temperature will be measured using the thermometer provided and the diameter of induration will be measured with the tape measure provided.

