10.5.5 Solicited AEs

For the Solicited AE analysis, data collected on both the eDiary (*Solicited Adverse Event*) and the CRF (*Local/Systemic Reactogenicity*) will be summarised together using the maximum reported intensity grade from either source.

Post-vaccine assessments on the day of the first vaccination and up to and including 7 days post-vaccination will be summarised under the First vaccination, and post-vaccine assessments on the day of

the second vaccination and up to and including 7 days post-vaccination will be summarised under the Second vaccination. This is the 7-day reactogenicity period. Pre-vaccine assessments for the first and second vaccination will not be included in the summaries and will be listed only.

The severity values will be mapped from the two sources as shown in Table 5. For erythema, induration, and fever, the eDiary values will be mapped to the intensity grades as described in Section 10.5.5.1.

Table 5 Solicited AE Severity

Severity	Solicited AE (eDiary) categories	Local/systemic reactogenicity (CRF) categories
Grade 0	0 – None	None
Grade 1	1 – No interference with activity	Mild
Grade 2	2 – Some interference with activity	Moderate
Grade 3	3 – Significant; prevents daily activity	Severe
Grade 4	4 – ER visit or hospitalisation	Life Threatening

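### The solicited-reaction denominator admits participants with no diary, so any missing diaries pull reactogenicity rates down by a factor that the plan does not let a reader assess

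*SAP*

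**What the plan says.** SAP 12.7.2.2 gives the number and percentage of participants with each solicited symptom, and the same by maximum severity, for each vaccination and overall. One sentence sets the denominator for both tables: "Percentages for both analyses are based on the number of participants reporting the severity of any solicited symptom on any day". The days that count run from dosing to 7 days after it.

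SAP 10.5.5 defines what falls in that period. eDiary and CRF reactogenicity records "will be summarised together using the maximum reported intensity grade from either source". Clinic checks on the dosing day count: "Post-vaccine assessments on the day of the first vaccination and up to and including 7 days post-vaccination will be summarised under the First vaccination", with a matching rule for the second vaccination. Table 5 of that section maps None, from either source, to Grade 0.

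The protocol supplies the records. Section 6.2 schedules a check for every vaccinee on each dosing day: "Local and systemic reactogenicity will be assessed at the end of the observation period", after at least 30 minutes. For the following days, Section 7.4.1.1 relies on the diary: "Solicited adverse events will be collected daily in the eDiary for 7 days post-vaccination". Table 2 (footnote [c]) and Section 6.3.2 add a reactogenicity assessment at the Day 7 or Day 35 clinic visit. Table 2 also marks reactogenicity at the Day 1 and Day 29 telephone calls, but Section 6.3.1 describes those calls only as diary reminders.

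**The concern.** A denominator limited to participants who reported is meant to leave out those with no data. Here it hardly can. The post-dose form alone qualifies a participant, even if every item on it is None. It qualifies that participant for all twelve solicited symptoms, because the rule is not symptom-specific. Someone observed for about half an hour and then without a diary until the Day 7 or Day 35 visit is counted as observed for the week.

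Any resulting error is downward, which is the unfavourable direction for a safety endpoint. Reactogenicity is named in the first primary endpoint, although SAP 12.7 places these tables under other safety endpoints. The table by intensity grade is also on the list of DMC and interim outputs in SAP 16.0.

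**Working it through.** **The plan's own figure.** The plan states no solicited-reaction rate. Its one safety calculation (Protocol 10.1, SAP 8.1) is an 80% chance of seeing a severe or serious event of 10% incidence in 16 participants. This reproduces: 1 − 0.9^16 = 0.815. It is not in dispute here.

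**Does a None entry count as a reported severity?** SAP 12.7.2.2 does not say so outright. "The severity values will be mapped from the two sources as shown in Table 5", and that table includes Grade 0. Section 12.7.2.2 also describes participants with a symptom as those "reporting a severity Grade 1 or higher", which implies that a severity below Grade 1 can be reported. If only Grade 1 or higher counted, the denominator would be limited to participants who had some reaction, which cannot be intended.

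**Does another rule remove a participant with no diary?**
- SAP 10.8: missing values are not replaced, so an absent diary simply adds no event.
- SAP 10.5.5.1: records with missing intensity are left out of the count of events; the denominator is not mentioned.
- SAP 10.10: the sensitivity analysis restores duplicate records; it does not address absent ones.
- No minimum diary requirement and no diary-completeness table is specified.

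None of them does.

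**Size.** Let p be the true 7-day rate, m the share of the denominator without a diary, and c the share of those participants' reactions that clinic checks record. With non-completion unrelated to reactions:

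expected reported rate = p × [(1 − m) + m × c] = p × [1 − m(1 − c)]

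The group sizes come from the plan: 16 planned for Groups 2 and 3, and 10 and 9 in the closed Groups 1 and 4 (SAP 8.1). The values of p, m and c are assumptions, with c run over its full range.

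| No diary | Factor, c = 0 | Factor, c = 0.5 | Factor, c = 1 | p = 60% reported as (c = 0 / 0.5 / 1) |
|---|---|---|---|---|
| 1 of 16 | 0.938 | 0.969 | 1 | 56.3% / 58.1% / 60% |
| 2 of 16 | 0.875 | 0.938 | 1 | 52.5% / 56.3% / 60% |
| 3 of 16 | 0.813 | 0.906 | 1 | 48.8% / 54.4% / 60% |
| 4 of 16 | 0.750 | 0.875 | 1 | 45.0% / 52.5% / 60% |
| 1 of 10 | 0.900 | 0.950 | 1 | 54.0% / 57.0% / 60% |
| 1 of 9 | 0.889 | 0.944 | 1 | 53.3% / 56.7% / 60% |

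An assumed example in counts: 16 vaccinated, 13 diaries, fatigue in 8 of the 13, and None at every clinic check for the other 3. The SAP rule prints 8/16 = 50%; among diary keepers it is 8/13 = 61.5%.

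**Checking the remedy.** It is tempting to use diary keepers plus anyone with a CRF-recorded event. That makes inclusion depend on the outcome. With p = 60%, 4 of 16 without a diary and c = 0.8:
- Expected events: 12 × 0.6 + 4 × 0.6 × 0.8 = 7.2 + 1.92 = 9.12.
- Present SAP rule: 9.12/16 = 57.0%.
- Diary keepers plus CRF events: 9.12/(12 + 1.92) = 65.5%, further from 60% than the present rule.
- Diary keepers only, in numerator and denominator: 7.2/12 = 60%.

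**The case against.** The strongest reply is that the clinic checks are more than the post-dose observation. The Day 7 or Day 35 visit includes a reactogenicity assessment, and SAP 10.5.5 pools CRF records up to and including day 7 at the maximum grade. If that visit takes a good history of the week, c could be near 1 and little is lost. This stands as a limit on size. The documents do not say whether the assessment is a finding on the day or recall over the week. A visit one day late, which the ±1-day window allows, falls outside the 7-day period.

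Second, the tables are descriptive and the groups small. In the example, exact 95% intervals are 25% to 75% for 8/16 and 32% to 86% for 8/13, so the shift lies well within sampling error. That is true, but the shift has a known direction and more precision would not remove it. Counts and the eDiary, CRF and combined listings are planned, so a careful reader could reconstruct the gap; the printed percentages would not show it.

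A reader might infer more than the documents support:
- That the rates are in fact understated. No diary completion figure is given, and with complete diaries the bias is zero.
- That every participant without a diary counts as symptom-free. That holds for a symptom only where no clinic check records Grade 1 or higher.
- That the bias differs by group or dose. Diary provision and reminders are the same for all groups, and nothing in the documents points to a difference.

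**Conclusion.** The point holds as a conditional one. As written, the rule puts essentially every vaccinee with a completed post-dose form into every symptom's denominator, diary or not, and no other rule corrects this. If diaries are missing and clinic checks do not recover all the reactions, the percentages are too low by the factor 1 − m(1 − c). In a group of 16 with one to four diaries missing, that is a relative loss of 6% to 25% at c = 0, 3% to 12.5% at c = 0.5, and none at c = 1. In the closed groups, one missing diary costs 10% to 11% at c = 0 and 5% to 6% at c = 0.5. These sizes rest on assumed m and c, on non-completion being unrelated to reactions, and on None counting as a reported severity, which Table 5 supports but 12.7.2.2 does not state. The plan should be changed because the correction is cheap and the planned summary tables do not show diary completeness.

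**What to change.** Replace the denominator sentence in SAP 12.7.2.2 with a rule to this effect:

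- For each symptom and vaccination, the denominator is the participants with at least one post-vaccination eDiary entry for that symptom within the SAP diary window (Day 0 to Day 7, or Day 28 to Day 35), whatever its grade.
- The numerator counts events, at the maximum grade from either source, only in those participants.
- Nobody joins the denominator because of having had an event. CRF-only events in participants without a diary are reported as a separate count.
- The present denominator is kept as a side-by-side sensitivity table.
- By group and vaccination, print the number with no diary and the diary days completed. This matters because one entry still qualifies, so partly kept diaries remain in the denominator.

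While the text is open, reconcile SAP 10.5.5 (maximum grade from either source) with SAP 10.10 (CRF record chosen when date and time match), since the second can lower a grade.

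The cost is SAP wording, a reprogrammed denominator and one short table, all on data already collected. The downside is a slightly smaller n per symptom. The new rate is free of this bias only if non-completion is unrelated to reactions, which is a further reason to show both denominators.
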